4.2. Required Behavior

If the participant is prescribed antibiotics or any other medications for any reason, they should report this prescription and they will be withdrawn from the trial as of the prescription date.

Participants are asked not to ingest or take any other form of cold remedy (over-the-counter (NyQuil/Dayquil/Cough Syrup/Cough Drops/EmergenC/Airborne/Zarbee's or any similar cold-relief product or prescription drugs) during the 18-day study period. If taken during the study duration the participant will record this as part of their diary and will be exited from the study.

Because none of the active ingredients are aimed at pain relief or reducing fever, participants will be allowed to take pain relievers/fever reducers (Advil/Tylenol or their equivalent).

Participants are asked to limit the consumption of alcohol beverages to less than or equal to two drinks per day and avoid recreational drugs or use of cannabis during the study period.

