- At time of enrollment, participant will be given access to the HIPAA compliant study portal.
 - The study portal provides access to study information, signed informed consent form, instructions for product use, frequently asked questions, study surveys, symptom diary, and data collection tools.
- Participant shall complete baseline assessments upon access to the portal.
 - Baseline assessment will include questions regarding the participants' demographics, medications, detailed information regarding previous colds, including treatment.
- To ensure that baseline assessments are completed before test product is used by the
 participant, study materials and study welcome package will be shipped to the participant once
 the clinical study manager/clinical operations coordinator confirms that the baseline assessment
 has been completed.
- The welcome package will include an information sheet that will outline instructions for their participation in the trial, the test product, disposable thermometer, and paper forms of the

- documents (paper form of study documents will be provided for real time data collection, in the event that the participant cannot log into the study portal to input data).
- Once the participant receives the test product, the participant will log into the study portal to acknowledge the receipt of the test product.
- Study start date will be the date of acknowledgement of receipt of test product.
- Participant will be sent weekly email reminders that remind them of their participation in the study. Once the participant indicates they are experiencing a cold. The participant will be reminded by email daily to complete their symptom diary.
- At the onset of their cold symptoms, the participant will complete the cold start form.
 - Onset is defined as the point in time the participant experiences 2 or more cold symptoms (cough, hoarseness, muscle ache, nasal drainage, scratchy throat, sore throat, sneezing, oral temperature greater than 37.7°C (99.9 °F)).
 - If fever is a symptom that the participant experiences, they will use the provided disposable thermometer to take their temperature and record it in the diary.
- If the participant meets all the criteria for a cold, they will start their symptom diary prior to taking the test product.
- After completing the surveys, the participant will take the test product. The participant will mix 1 drink-mix packet into 6-8 oz of water and consume the whole drink.

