13.1.4. Appendix D Baseline Form

Baseline

- 1. Demographics
 - a. Race/Ethnicity (Black or African American, White, Asian, American Indian or Alaska Native, Native Hawaiian or another pacific islander, other: _____, do not want to share)
 - b. Sex (M, F, or Do not want to share)
- 2. On average how many colds do you get a year?
- 3. On average How long do your colds usually last? (1-3 days, 4-6 days, 7-9 days, >10 days)
- 4. When you have a cold what Cold Symptoms do you usually experience? (check all that apply)
 - a. Cough
 - b. Hoarseness
 - c. Muscle aches
 - d. Runny Nose
 - e. Nasal Congestion
 - f. Scratchy Throat
 - g. Sore throat
 - h. Sneezing
 - i. Oral Temp > than 37.7 °C (99.9 °F)
 - j. Other:
- 5. Do you take any medication when you have a cold (i.e. Dayquil/Nyquil, Advil, or Prescription etc.)?
 - a. If so, which medications do you take?
 - b. How often do you normally take them? (once a day, as needed, or as instructed)
 - c. Are they successful in treating your symptoms?
- 6. Do you take any supplements when you have a cold (Emergen-C, Vitamin C, Airborne, Nettipot, etc.)?
 - a. If so, which supplements do you take?
 - b. How often do you take the supplement when you have a cold? (once a day, several times a day, every other day, once in a while)
 - c. Are they successful in helping with your symptoms?

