13.1.5. Appendix E Symptom Diary

Daily Symptom Survey

BEFOREtaking the test product OR any allowed medication, please answer all of the following questions daily for the duration of your cold symptoms.

REMINDER: DURING THE TRIAL, YOU ARE NOT ALLOWED TO TAKE ANY COLD MEDICATIONS (NYQUIL/DAYQUIL, TYLENOL COLD, COUGH SYRUP/LOZENGES, ETC.)

1. Cough			
0	1	2	3
No Symptom	Slight	Moderate	Severe
2. Hoarseness			
0	1	2	3
No Symptom	Slight	Moderate	Severe
3. Muscle aches			
0	1	2	3
No Symptom	Slight	Moderate	Severe
4. Runny Nose			
0	1	2	3
No Symptom	Slight	Moderate	Severe
5. Nasal Congestion			
0	1	2	3
No Symptom	Slight	Moderate	Severe
6. Scratchy Throat			
0	1	2	3
No Symptom	Slight	Moderate	Severe

7. Sore throat

0	1	2	3
No Symptom	Slight	Moderate	Severe
8. Sneezing			
0	1	2	3
No Symptom	Slight	Moderate	Severe

- 9. Did you take any pain/fever reducer (ibuprofen/acetaminophen today? (Y/N)
 - a. Why?
 - b. Did it work? (Y/N)
- 10. Have you taken any other cold medications (Nyquil, Dayquil, other cold medication, cough drop, cough syrup, etc.)? (Y/N)
 - a. If yes, please exit from the study
- 11. Have you seen a doctor for your symptoms? (Y/N)
 - a. If yes, were you prescribed anything? $(Y/N) \rightarrow$ if yes please exit from the study
- 12. Did you experience any side effects after taking the product? (Y/N)
 - a. If yes, please fill out the Adverse Event form.

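### The diary question that enforces the ban on other cold remedies asks only about cold medications, so users of barred supplements may go unidentified in the primary curve

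*Combined protocol and SAP*

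**What the plan says.** The rule is in Section 4.2: "Participants are asked not to ingest or take any other form of cold remedy". The products listed there include "NyQuil/Dayquil/Cough Syrup/Cough Drops/EmergenC/Airborne" and Zarbee's, with a catch-all for similar products. The same section sets out how the rule is enforced: "If taken during the study duration the participant will record this as part of their diary and will be exited from the study".

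The diary in Appendix E opens with a reminder that "YOU ARE NOT ALLOWED TO TAKE ANY COLD MEDICATIONS (NYQUIL/DAYQUIL, TYLENOL COLD, COUGH SYRUP/LOZENGES, ETC". Item 10 then asks: "Have you taken any other cold medications (Nyquil, Dayquil, other cold medication, cough drop, cough syrup, etc". A Yes leads to item 10a: "If yes, please exit from the study". No product name is requested.

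The baseline form (Appendix D) treats the two kinds of product as separate categories. Item 5 asks about medication, with Dayquil/Nyquil, Advil and prescriptions as examples. Item 6 asks: "Do you take any supplements when you have a cold (Emergen-C, Vitamin C, Airborne, Nettipot, etc".

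Under Section 7.1 the primary Kaplan-Meier analysis includes everyone who consented, reported a cold and took at least one dose. Section 7.3 censors participants who withdraw, and those whose daily reports stop early. It does not mention use of a barred remedy by name.

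**The concern.** The diary is the instrument that Section 4.2 relies on, and its question is narrower than the rule. A participant who takes Emergen-C during the study cold, and who has already seen it labelled a supplement on the baseline form, can honestly answer No to a question about medications. That person is not exited and stays in the primary curve. Another participant who does the same thing but reads the question broadly answers Yes and leaves.

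The study population makes this a practical matter. Section 5 recruits people who want herbal remedies for colds, and baseline item 6 anticipates that some of them take supplements when ill. At stake are knowing who was co-treated during the study cold and applying the Section 4.2 rule in the same way to everyone. The protocol also says the data may help design a later two-arm trial, where the rate of other-remedy use would be a useful input.

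**Working it through.** **1. Rule against instrument.**

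| Source | Term used | Emergen-C, Airborne or Zarbee's named? |
|---|---|---|
| Section 4.2 | any cold remedy | all three |
| Appendix D, item 5 | medication | none |
| Appendix D, item 6 | supplements | Emergen-C and Airborne |
| Appendix E, reminder | cold medications | none |
| Appendix E, item 10 | cold medications | none |

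**2. Does another form fill the gap?** Diary item 9 covers ibuprofen and acetaminophen, item 11 covers doctor visits and prescriptions, and item 12 covers side effects. The exit form (Appendix F) and adverse event form (Appendix G) do not ask about other remedies. The schedule in Section 6.2 marks medications and supplements only before the product arrives. No in-study form in the text reviewed asks about supplements.

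**3. What a Yes already provides.** The diary is completed daily, so the first Yes dates use to the interval since the previous entry, about one day if diaries are complete. The product is what is missing.

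**4. How many could be missed.** The plan's own figure reproduces: 200 × 0.40 = 80 participants with colds (Section 7.2). The documents give no rate of supplement use or of misreading, so both are assumed.

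- Users: 80 × 0.10 = 8 to 80 × 0.30 = 24.
- Missed: 8 × 0.25 = 2 to 24 × 1.00 = 24.

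**5. Illustration of the median; every input is assumed.** Take Weibull time to resolution with shape 2 and median 7 days, so H(t) = ln 2 × (t/7)². Let a share q of participants use a supplement from day 3 if still ill (exp(−H(3)) = 0.88 of them are), with their resolution hazard multiplied by r from then on. Detected users are censored at day 3. With every user detected, the median is 7.00. With every user missed, it solves

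(1 − q)·exp(−H(t)) + q·exp(−H(3) − r·[H(t) − H(3)]) = 0.5.

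| q | r = 0.67 | r = 1 | r = 1.5 |
|---|---|---|---|
| 10% | 7.11 | 7.00 | 6.88 |
| 30% | 7.33 | 7.00 | 6.65 |

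The largest shift is about a third of a day, in either direction. It needs 30% use, a real effect and every user missed. In the same model the simulated 95% sampling range of a median from 80 participants is about 5.9 to 8.1 days.

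**6. Would full detection make the median more accurate?** Not necessarily. Suppose users simply have worse colds from onset (hazard × 0.67) and the supplement does nothing. With 30% users the true median is 7.41 days, and censoring all of them at day 3 gives 7.06. With 10% users the values are 7.13 and about 7.0.

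**The case against.** The strongest reply has four parts.

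- **Item 10 is open-ended.** Its list ends in an etc., and participants may be told the full ban elsewhere. Section 6.1 says "At the onset of their cold symptoms, the participant will complete the cold start form", and it also mentions an information sheet and frequently asked questions. None of these is in the text reviewed, and the consent pages were removed. This stands as a limit: misreporting is a risk and has not been shown. It does not change what item 10 asks.
- **Reliance on self-report is disclosed.** Section 11 admits that compliance is not independently checked. That covers the lack of verification. It does not cover a self-report question narrower than the rule it serves.
- **Keeping users in the curve fits the population definition.** Section 7.1 requires only consent, a cold and one dose, and step 6 shows that censoring users can move the median away from the truth. This stands, and it is why no gain in accuracy is claimed.
- **Most co-treatment is already recorded.** Items 9 to 11 cover pain relievers, cold medications and prescriptions, and the daily entries date a first Yes. This stands. A reader might infer that co-treatment during the cold cannot be reconstructed, or that timing of use is lost. The diary does not support either reading; the loss is confined to supplement users who answer No, and to product names.

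**Conclusion.** The mismatch between Section 4.2 and the diary is plain in the text. Its consequence is a possibility of unknown frequency: some users of barred supplements may answer No and remain in the primary curve unidentified.

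A reader might go further and conclude that the exit rule is in fact applied unevenly, or that the primary median is biased. The documents support neither. They give no rate of use, no rate of misreading and no effect of co-treatment, so the direction and size of any shift cannot be determined. The counts of 2 to 24 and the shifts of up to about a third of a day only show scale under assumed inputs. They also treat exit under Section 4.2 as censoring, which is the natural reading of Section 7.3 but is not stated there.

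The study is single-arm and descriptive, with no formal comparison against historical results, so this is a minor point. The change is worth making because it costs almost nothing.

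**What to change.** - Reword the reminder and item 10 to ask about *any other cold remedy, including medications, vitamins, supplements or herbal products (e.g. NyQuil, DayQuil, cough drops, Emergen-C, Airborne, Zarbee's)*. Leave the permitted pain and fever reducers in item 9.
- Add a product-name field to item 10a, completed before exit.
- Take the date of first use from the daily diary entry on which item 10 is first answered Yes; no separate date field is needed.
- Report the number of users alongside the primary curve.

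The cost is two reworded texts and one short field in the eDiary, with the form change notified to the IRB. The diary becomes slightly longer, and a few more participants may be exited and censored. The loss of precision is small: in the illustration, censoring 30% of participants as users at day 3 widens the 95% sampling range of the median from about 5.9–8.1 to about 5.8–8.3 days. In return, co-treatment is identified and the Section 4.2 rule can be applied evenly.

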6.4. Adverse Event and Safety Monitoring

Adverse Events (AEs) are defined as any untoward medical occurrences described by the study participant. All AEs will be self-reported and documented on the platform. The AEs will be reviewed by the study team including the remote trial coordinator and study principal investigator and reported according to the IRB requirements. Participants who experience adverse events will be advised to stop taking the test product and seek medical attention.

In the event that a participant experiences an adverse event, the clinical study manager or clinical ops coordinator will notify both the PI and Sponsor. The Sponsor will take appropriate action according to their standard operating procedures for any adverse events that warrant action by the sponsor.

6.4.1.Anticipated Adverse Events

Anticipated Adverse Events are complications that are known to be associated with the test product (in high doses exceeding recommended use):

- epigastric pain
- nausea
- vomiting
- loss of appetite
- abdominal cramps
- diarrhea
- headaches

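### In the symptom diary the exit instructions come before the side-effect question, so participants who leave early may not answer it on their last entry

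*Combined protocol and SAP*

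**What the plan says.** **Diary (13.1.5, Appendix E).** The header asks participants to complete the form before that day's product or any allowed medication: "please answer all of the following questions daily for the duration of your cold symptoms". Items 1 to 8 score symptoms and item 9 asks about pain or fever reducers. Item 10 asks about other cold medications, and its sub-item reads "If yes, please exit from the study". Item 11 asks "Have you seen a doctor for your symptoms? (Y/N)", and 11a directs anyone who was prescribed something to exit. Item 12, the last on the form, asks "Did you experience any side effects after taking the product" and sends a Yes to the Adverse Event form.

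**Exit rules (4.2).** On other remedies: "If taken during the study duration the participant will record this as part of their diary and will be exited from the study". On prescriptions: "they will be withdrawn from the trial as of the prescription date".

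**Other safety capture.** Section 6.1 has a standing instruction to complete an Adverse Event form for any side effect after taking the product. The schedule in 6.2 marks both the Symptom Diary and the AE assessment at event start, on Days 1-18 and at study exit. Section 6.4 makes all adverse events self-reported and adds: "Participants who experience adverse events will be advised to stop taking the test product and seek medical attention". Sections 3 and 7.1 list the adverse event summary among the secondary endpoints.

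**The concern.** Two instructions to leave the study stand between the participant and the only side-effect question in the diary. Someone who treats them as the end of the task stops at item 10a or 11a and leaves item 12 blank.

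That entry matters because of its timing. The diary is filled in before the day's product, so item 12 on a given day can only concern packets already taken, and the last entry is the diary's one chance to ask about the most recent ones. The first entry comes before any packet (sections 4 and 6.1). A participant who leaves at the second entry without reaching item 12 will therefore never have answered a diary side-effect question after dosing.

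At stake is the completeness of the adverse event summary, the trial's only safety result, in a group defined by having left early. All events are self-reported and section 11 acknowledges that there is no medical review of symptoms, so an event that nobody asks about may never be recorded.

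**Working it through.** The plan states no figure on this point, so there is none to reproduce. The check follows a participant who exits for another remedy or a prescription and asks where the documents put a side-effect question to that person.

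1. **Diary, last entry.** The order is 10, 10a (exit), 11, 11a (exit), 12 (side effects). The header says to answer everything, while 10a and 11a say to exit. No skip logic is shown, and nothing tells the participant to finish the form first. Item 12 may or may not be answered.
2. **Study Exit Form (13.1.6).** Its five items cover overall experience, perceived help with the cold, likelihood of recommending, help in coping with the elements, and an open comment on taste, smell, consistency or other matters. None asks about side effects.
3. **Prompt for the exit form (6.1).** The email is described for complete resolution or after 18 days. The exit footnote to the 6.2 schedule lists resolution, 18 days, or 90 days without a cold. Neither mentions exit for a remedy or a prescription. Section 6.5 has the exit form completed for people who cannot be reached, which does not put a question to them.
4. **Adverse Event form (13.1.7).** Its item 1 asks about side effects after the product, and section 6.1 instructs its use. This route stays open, but the participant has to start it.
5. **Schedule (6.2).** An AE assessment is due at study exit. Set against steps 1 to 4, no prompted question reliably delivers it for this exit route.

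**Size.** Let *e* be the share of treated participants who exit through 10a or 11a, *a* the chance of an event since the previous entry, and *s* the share of those with an event who neither answer item 12 nor use the Adverse Event form. Missed events = 80 × *e* × *a* × *s*, where 80 is the desired number of treated participants (5.1). The documents give none of *e*, *a* or *s*. With assumed values and the extreme *s* = 1:

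| *e* (assumed) | Exiters | *a* = 2% | *a* = 5% | *a* = 20% |
|---|---|---|---|---|
| 10% | 80 × 0.10 = 8 | 0.16 | 0.4 | 1.6 |
| 25% | 80 × 0.25 = 20 | 0.4 | 1.0 | 4.0 |

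The result runs from 0.16 to 4 events, or 0.2% to 5% of 80, and shrinks in proportion as *s* falls below 1. A 25-fold spread produced by assumptions alone is not an estimate. It shows only that the documents do not fix the size.

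**The case against.** The strongest reply is that the question is asked. Item 12 is on the same form, the header covers all items, and 10a and 11a speak of leaving the study, not of abandoning the page. Section 4.2 can be read as the study team exiting the participant after the use has been recorded. The portal's branching is not visible in the documents. Section 6.1 separately instructs use of the Adverse Event form, and section 6.3 allows a coordinator to chase incomplete forms. All of this stands, and it limits the point to what participants *may* leave unanswered. It does not remove the point: the header competes with a later, more specific instruction, paper copies (6.1) cannot force anyone on to item 12, and the coordinator's prompt is optional and not specific to side effects.

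Two stronger readings are tempting, and the documents support neither.

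- A reader might infer that these leavers are the people most likely to have had an adverse event. Items 10 and 11 capture other cold medication and a doctor visit for symptoms, which point first to a worse or longer cold. Section 6.4 does suggest a path from an adverse event to medical attention, and a prescription could follow. But that advice comes after text on events being reported and reviewed, so a person who receives it has probably reported already. The Adverse Event form also has its own question on doctor or hospital visits. The link is inference.
- A reader might infer that 2 to 4 events would be lost. That needs a 20% event chance in what is usually about one day, every exiter with an event skipping item 12, and none using the Adverse Event form. It is the top of the assumed range, not an expectation.

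**Conclusion.** The point holds as a possible gap in adverse event capture at early exit. The diary places its exit instructions before its side-effect question, the exit form does not ask the question, and that form's prompt is not described for exits due to a remedy or prescription. This falls short of the AE assessment that the schedule marks at study exit. Any effect would be an under-count among early leavers; its size cannot be derived from the documents. The conclusion assumes only that some participants act on an exit instruction when they read it. It does not show that events will be lost, that investigator review will be delayed, or that these participants carry a higher event rate. It is a low-cost improvement to the form and leaves the primary analysis untouched.

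**What to change.** In Appendix E, move item 12 above item 10 and ask about side effects *since your last entry*, with a not-applicable choice on the first entry, which precedes any product. Reword 10a and 11a so that the participant completes all items, and the Adverse Event form if the side-effect answer is Yes, before exiting. Leave the exit rules themselves as they are.

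Optionally, add the same question to the Study Exit Form and extend its prompt in section 6.1 to every exit reason. That would give the schedule's AE assessment at exit a definite home.

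The cost is a reordering and a few words in the electronic diary and its paper copy, plus one item and one prompt trigger if the optional part is adopted. Sample size and analysis do not change.

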2.2.3. Minimization of Risks

Research participants will be carefully screened to meet enrollment criteria. Participants meeting exclusion criteria will not be enrolled. The study participant informed consent will be presented with clear description of the study requirements and opportunity to have questions answered before enrollment will be provided. Once an event occurs, review of symptoms will be

ascertained daily until symptoms have resolved or for 18 days. Reporting of adverse events will be reviewed routinely and in accordance with regulatory guidelines (21CFR, GCP) by the Principal Investigator. Participants with occurrence of worsening symptoms or adverse events will be advised to stop the product and may seek medical attention and exit the study.

3. Study Objectives

The purpose of the present study is to evaluate 1) the impact of the Immune Support test product on the duration of symptoms of the common cold in adult participants and 2) the subjective experience of these participants related to general health, common cold symptoms, and personal experience with the product. [13, 18, 29, 32]

This will be evaluated based on the primary and secondary endpoints. These endpoints, the analysis populations, and their respective measures are described below. Further details on the methods for measuring the outcomes can be found in the Study Outcome Measures and Analysis Plan sections.

Primary Endpoint:

The primary endpoint will be time to freedom from cold symptoms, with the clock starting at the onset of the cold. Where the onset is defined as the point in time when the participant experiences 2 or more cold symptoms. The primary analysis will be a Kaplan-Meier analysis of time to absence of all symptoms, based on the participants' self-report. There is no control group for the primary analysis. [5]

Secondary Endpoint:

- Secondary endpoints involve the duration and severity of the separate cold symptoms.
- Comparison against the participant's normal behavior.
- Net Promoter Score.
- Adverse events will be summarized.
- An additional data presentation will consist of results from both Treatment and Control in similar studies appearing in the literature. There will be no formal statistical comparison of results from this study and historical studies.

4.Study Design

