- Participant will take the test product twice a day, at least 4-6 hours apart.
- The next day the participant will complete their symptom diary prior to taking the test product. Once completed they will mix 1 packet of the test product into 6-8 oz of water and consume the whole drink. They will take the test product again 4-6 hours later.
- The participant will complete this process daily until their cold symptoms resolve or for 18 days, whichever is shorter.
- If the participant takes ibuprofen or acetaminophen at any time, the participant will record this on their symptom diary.
- After taking the test product, the participant will be instructed to fill out an Adverse Event form for any side-effects experienced.
- The participant will be prompted, by email, to complete the study exit form once the participant's symptoms resolve completely or after 18 days, whichever is shorter.
- Neither the sponsor nor Hawthorne Effect, Inc. will make any attempt to collect any unused test product.
- Upon receipt of study exit survey and review of completed study forms, participant will receive an Amazon gift card of \$25 via email.

6.2.Study Schedule of Activities

Assessments	Screening	Consent	Before Receipt of Test Product	Product Received	Event Start Date**	Days 1-18*	Study Exit***
Study Window							
Screening Survey	Х						
Consent		Х					
Baseline Survey			х				
Demographics			х				
Acknowledgement of Receipt of Test Product				Х			
Test Product Consumed****					Х	Х	
Symptom Diary					Х	Х	Х
Meds & Supplements			Х				
AE Assessment					Х	Х	Х
Study Exit Survey							Х

^{*}Participant will participate in the study starting on the day of the cold until the cold symptoms resolve or 18 days whichever is shorter.

^{**} The day the participant experiences 2 or more of the protocol defined symptoms

^{***} The participant will exit the study at the time of complete cold symptom resolution, 18 days after the start of cold symptoms, or at 90 days if no cold is experienced by the participant.

^{****} The product will be consumed twice a day, 4-6 hours apart

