6.4.2. Adverse Event Relationship

Each reported AE will be assessed by the Investigator for relatedness, severity and causality.

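### The AE prompts ask only about side effects, which is narrower than the AE definition in section 6.4, so the AE summary may lean towards events that participants blame on the product

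*Combined protocol and SAP*

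**What the plan says.** The definition in section 6.4 is broad: "Adverse Events (AEs) are defined as any untoward medical occurrences described by the study participant". The same section says that all AEs are self-reported. Section 6.4.2 puts the causal judgement after reporting: "Each reported AE will be assessed by the Investigator for relatedness, severity and causality". Section 2.2.3 adds a review step: "Reporting of adverse events will be reviewed routinely and in accordance with regulatory guidelines".

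The collection tools use a different term. In section 6.1, once the product has been taken, "the participant will be instructed to fill out an Adverse Event form for any side-effects experienced". Item 12 of the symptom diary (Appendix E) asks "Did you experience any side effects after taking the product? (Y/N", and a yes leads to the AE form (Appendix G). Item 1 of that form puts almost the same question again.

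The schedule in section 6.2 lists an AE assessment at event start, on Days 1-18 and at study exit, without giving its wording. Section 7.3 says only that AEs will be summarized and leaves detail to an SAP still to be written.

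**The concern.** To a participant, a side effect is something the product caused. The prompts therefore invite the participant to judge relatedness first, and the investigator sees only what passes that judgement. A cold can itself plausibly explain a headache, mild nausea or poor appetite, so an honest no is easy to give.

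The wording matters more here than in a clinic-based trial. There are no site visits, and section 11 states that symptoms receive no medical review. AEs are a listed secondary item, there is no control arm, and the data may help to design a two-arm trial. A table presented as AEs under 6.4 but collected as suspected side effects could mislead that later design about the background of events to expect.

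**Working it through.** The plan states no AE rate, so there is no figure to reproduce. The check sets the definition beside each place where an AE could be reported.

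1. **Definition (6.4).** Any untoward occurrence that the participant describes. No causal link is required.
2. **Relatedness (6.4.2).** Judged by the investigator, for reported AEs.
3. **Instruction (6.1).** The AE form is for side effects.
4. **Daily trigger (Appendix E, item 12).** Asks about side effects after taking the product.
5. **Entry to the AE form (Appendix G, item 1).** Asks about side effects. The tick list, including its Other line, follows only if the answer is yes.
6. **Rest of the AE form.** Items 3, 4 and 5 say side effect; item 2 says event. With item 1, that is 4 of 5 items. Item 5 asks about hospital or doctor contact only for the side effect.
7. **Exit form (Appendix F).** 0 of 5 items ask about AEs. Item 5 is an open question about experience with the product. The schedule nevertheless lists an AE assessment at exit.

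Steps 3 to 5 form one reporting chain, so they are one mismatch and not three.

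Follow one event through. A participant has a headache on a diary day and blames the cold. Headache is not among the eight scored diary symptoms. At item 12 the participant can reasonably answer no, and the AE form is not opened. If a pain reliever was taken, the reason may appear as free text at item 9a. Otherwise no form in the supplied text asks about the headache. Diary item 11 asks about doctor visits for symptoms, but it does not lead to the AE form.

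The tick list helps little with milder events. Section 6.4.1 introduces its terms as follows: "Anticipated Adverse Events are complications that are known to be associated with the test product (in high doses exceeding recommended use". It names seven. Against the AE form:

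- Listed plainly: 1 (loss of appetite).
- Listed only as severe and persistent: 5 (nausea, vomiting, diarrhea, and epigastric pain and abdominal cramps under abdominal pain). This assumes that the qualifier covers all four terms in that line.
- Not listed: 1 (headaches).

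1 + 5 + 1 = 7. The form also has no item that asks for severity, which 6.4.2 requires the investigator to assess.

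On size, section 7.2 expects 200 × 0.40 = 80 participants with colds. Converting that into lost reports would need an all-cause AE rate and the share of participants who would blame the product. The documents give neither, so no number is offered.

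**The case against.** The best reply is that the gap is narrower than it looks. The definition in 6.4 itself depends on what the participant describes. The words after taking can be read as timing, so some participants will report any complaint that follows a dose. Item 12 leads to a form titled for adverse events. Its list includes signs that few people would call product effects, its Other line is open, and its item 2 asks for the event. Reviews of AEs (2.2.3, 6.4) and of the forms before the gift card is sent ("Upon receipt of study exit survey and review of completed study forms", in 6.1) could pick up something written elsewhere. Section 11 already discloses reliance on self-report. The cold start form is not in the text available for this review, and some parts of the document were not available either, so another AE question may exist.

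Much of this stands, and it limits the point to the supplied text and to a possible loss. It does not remove the point. The temporal reading leaves the word side effects in place. The Other line and item 2 sit on a form reached through the side-effect question. The reviews, and any later SAP, can use only what was written down. The general statement in section 11 does not tell a reader that the AE table was collected on a narrower question than the definition.

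Two stronger readings should be resisted. A reader might infer that events not blamed on the product are excluded from the AE record. Nothing in the text excludes them, and a participant may still describe them. A reader might also infer that AEs will be undercounted by some estimable amount, or that the efficacy result is in doubt. The documents support neither.

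**Conclusion.** The mismatch is in the protocol's own wording: a cause-free AE definition, a reporting chain that asks about side effects, and no AE question on the exit form despite an AE assessment scheduled there. As written, events that participants do not attribute to the product may go unreported, and the AE summary may lean towards participant-attributed effects. The direction is plausible and the size is unknown. No reported result is shown to change, and the primary time-to-resolution analysis as planned is unaffected.

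This rests on two assumptions: that a fair share of participants read side effects as caused by the product, and that no form outside the supplied text asks a broader question. Severity is minor.

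**What to change.** **Prompts.** Reword 6.1, diary item 12 and AE form items 1 and 3-5 to ask about any new or worsening health problem since starting the product, whether or not the participant thinks the product caused it. Say explicitly that this includes a scored cold symptom or fever that is unexpectedly severe. Put the same question on the exit form.

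**AE form.** List the seven 6.4.1 terms without the severe-and-persistent qualifier, and add a severity item.

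**Stop advice.** Leave it as it is in 6.4 and 2.2.3. Section 6.4 reads "Participants who experience adverse events will be advised to stop taking the test product and seek medical attention". That is a safety rule, and wider capture is no reason to loosen it.

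**SAP.** Report AEs by investigator-assessed relatedness. If the forms can no longer change, label the AE table as mainly participant-attributed side effects.

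**Cost.** An IRB amendment, updated electronic forms and some investigator time, with no new visits. More cold-related events will be reported across the roughly 80 treated participants, which is why the table should be split by relatedness. More participants may receive stop advice. If some then leave the study, section 7.3 censors them, so the number of such exits is worth watching.
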